M.I.N.I. KID	Mini International Neuropsychiatric Interview for Children and Adolescents
MDD	Major Depressive Disorder
MRI	Magnetic Resonance Imaging
MRS	Magnetic Resonance Spectroscopy
NIH	National Institutes of Health
PHI	Protected Health Information
PHI PI	
	Principal Investigator
QIDS-A17-SR	Quick Inventory of Depressive Symptoms – Adolescent Version – Self Report
TMS	Transcranial Magnetic Stimulation
SAE	Serious Adverse Event/Serious Adverse Experience
SOP	Standard Operating Procedure
SSRI	Selective Serotonin Reuptake Inhibitor
TASS	Transcranial Magnetic Stimulation Adult Safety Screen
TEEQ	Treatment Expectations and Experience Questionnaire
YMRS	Young Mania Rating Scale

Page 10 of 61

7 Study Summary

	I I I I I I I I I I I I I I I I I I I
Title	A Randomized, Sham-Controlled Trial of the Safety and Effectiveness of NeuroStar Transcranial Magnetic Stimulation (TMS) Therapy in Depressed Adolescents
Running Title	NeuroStar [®] TMS Adolescent MDD RCT
Protocol Number	44-02219-000
Methodology	Randomized, sham-controlled, triple-blinded; crossover open-label acute treatment and post treatment follow up. (Investigator Blinded to criteria for eligibility to entry into crossover study phase)
Overall Study Duration	42 months
	Screening to Randomization: 1 week
	Phase I (Randomized, Blinded): 6 weeks (Active TMS vs. Sham)
Subject Participation Duration	Phase II (Non-Randomized, Open-label): 6 weeks of open-label acute treatment (for Phase I subjects who did not receive protocol-defined clinical benefit). (Note: The definition of protocol defined clinical benefit is concealed from study staff.)
Duration	Taper (End of Phase I or Phase II): After acute treatment is completed (prior to exit of study at end of phase or prior to entry into Phase III), subject will receive 3 weeks of taper treatments (week 1:3, week 2:2, week 3:1
	Phase III (Long term follow up): 6 month follow up with retreatment course for symptom re-emergence (for Phase I and II subjects who received protocol-defined clinical benefit)
	Primary: To evaluate the antidepressant effects of daily, active TMS (when compared with sham treatment) in adolescents meeting criteria for Major Depressive Disorder, single or recurrent episode (Phase I).
	Secondary: To evaluate the acute and long term safety of TMS treatment in adolescent MDD subjects.
Objectives	To evaluate the durability of benefit of TMS treatment over the course of 6 months in subjects who received clinical benefit from acute treatment course(s) (Phase III).
	To evaluate the benefit of daily, active, open-label TMS in Phase I subjects who did not receive protocol-defined clinical benefit; as new acute treatment (sham to active) or as extended treatment course (blinded active to open label active) (Phase II)

	Structural MRI (conducted at specific sites only): To utilize standard morphometric measures to determine structural changes in the brain associated with TMS treatment.
	Phase I: Total of 100 enrolled (50 Active/50 Sham) across sites
Number of Subjects	 Phase II: Subjects from phase I who did not receive protocol-defined clinical benefit from acute treatment will be offered open-label treatment (estimated to be 42 subjects) Phase III: Subject who did meet protocol-defined clinical benefit after acute treatment in Phase I or Phase II will be followed for 6 months post taper (estimated to be 37 subjects) Structural MRI subset: Approximately 25% of subjects of the Phase I population.
Diagnosis and Main Inclusion Criteria	 Male or female outpatients, age 12-21, meeting DSM-5 diagnosis of Major Depressive Disorder, single or recurrent course of illness, of moderate or greater symptom severity CGI-S score ≥ 4 HAMD₂₄, item 1 ≥ 2 and total score at least 20 at screening At the end of the baseline visit, subject must have a HAMD24 score of ≥ 18 and change in score may not be ≥ 25% decrease from that seen at the screening visit Duration of current episode of depression ≥ 4 weeks and ≤ 3 years Resistance to antidepressant treatment in a discrete illness episode defined by the Antidepressant Treatment Record (ATR): Resistance to treatment defined by ATR level 1 through 4 in current episode. If insufficient number of trials in a previous episode Subjects who have been unable to complete an antidepressant trial of adequate dose and duration due to intolerance to antidepressant therapy may be included if they have demonstrated intolerance to ≥ 4 antidepressant medications within one discrete illness episode (current or a previous episode as defined above) For any subject currently receiving antidepressant medication, the clinician must determine that insufficient benefit is being received from this treatment and it is clinically appropriate to discontinue the existing antidepressant.
Exclusion Criteria	 Subjects associated directly with this study or indirectly by a parent or sibling being affiliated with the study. Subjects diagnosed by the investigator with one or more of the following conditions (current, unless otherwise stated): depression secondary to a general medical condition or substance-induced; seasonal pattern of depression; history of substance abuse or dependence within the past year (except nicotine or caffeine); any psychotic disorder (lifetime), including schizoaffective disorder, or major depression with psychotic features in this or previous episodes; amnestic disorder, mental retardation, bipolar disorder; eating disorder (lifetime); obsessive compulsive disorder (lifetime); or

	posttraumatic stress disorder (lifetime)
	• Any psychiatric disorder, which in the judgement of the Investigator may hinder the subject in completing the procedures required by the study
	protocol.
	• Subject with a clinically defined neurological disorder or insult including, but not limited to any condition likely increase the risk of seizure; such as, space occupying brain lesion; any history or family history of epilepsy;
	history of cerebrovascular accident; transient ischemic attack within two
	years; cerebral aneurysm; dementia; brain surgery or history of stroke.Increased risk of seizure for any reason, including prior diagnosis of
	increased fixed rescure for any reason, including prior diagnosis of increased intracranial pressure or history of significant head trauma with loss of consciousness for \geq 5 minutes.
	 A true positive response to any question on the TASS
	• Inability to locate and quantify a motor threshold as defined in the protocol
	• History of treatment with ECT or TMS Therapy for any disorder
	• Use of any investigational drug within 4 weeks of the baseline visit
	• Use of any excluded medication(s) listed on the Concomitant Medication List (Appendix D) within 1 week of the baseline visit
	 Significant acute suicide risk, defined as follows: Suicide attempt within the
	previous 6 months that required medical treatment or ≥ 2 attempts in the past 12 months, or has a clear cut plan for suicide and states that he/she cannot guarantee that he/she will inform a family member or call his/her psychiatrist
	or the investigator if the impulse to implement the plan becomes substantial during the study; or, in the investigator's opinion, is likely to attempt suicide within the next 6 months.
	• Conductive, ferromagnetic, or other magnetic-sensitive metals implanted in the subject's head within 30 cm of the treatment coil excluding the mouth that cannot safely be removed. Examples include cochlear implants, implanted electrodes/stimulators, aneurysm clips or coils, stents, bullet fragments, jewelry and hair barrettes.
	• Active or inactive implants (including device leads), including deep brain stimulators, cochlear implants, and vagus nerve stimulators.
	 Cardiac pacemakers, implanted medication pumps, intracardiac lines, or acute, unstable cardiac disease
	Known or suspected pregnancy
	• If sexually active female, not on an approved method of birth control.
	• Unstable psychotherapy (therapy must be for at least 3 months prior to entry into the study, with no anticipation of change in the frequency or treatment focus of the therapeutic sessions over the duration of the study)
	• Positive urine drug screen (a positive screen at screening may be repeated
	once prior to randomization upon approval from the Sponsor)
	 Clinically significant laboratory abnormality or medical condition, in the opinion of the Investigator would hinder the subject in completing the procedures required by the study.
	NeuroStar TMS Therapy [®] System using NeuroStar XPLOR [®] research
Study Device	configuration

	coil operates with an acoustically matched profile that renders the auditory experience of the treatments virtually indistinguishable to subjects or researchers. The sham coil also creates a mild percussive sensation that may be felt by the subject and further assists in simulating the active condition. The blinded randomization of patients in the Phase I acute phase to the active or sham condition will remain blinded for the duration of all study phases including Phases II and III.
Permitted: Zaleplon, zolpidem, or zopiclone (1 dose nightly) as need treatment emergent insomnia or lorazepam (up to 2 mg daily) for tr emergent anxiety, may be administered for up to 14 doses during Pl additional 14 doses during Phase II. For Phase III, these medication administered for up to 10 days, on ≤5 occasions. The use of alternation or anxiolytic compounds requires prior approval from the Sponsor. contraceptives are allowed if the subject has been on a stable dose for months. The use of alternative hypnotics or anxiolytic compounds requires prior approval from the Sponsor. Short-term treatments for headaches, a colds, or flu-like symptoms require prior approval from the Sponsor.	
	Prohibited: Any medication administered for the treatment of any psychiatric or neurologic disorder or any other known CNS-active drugs, including herbal, over-the-counter, and homeopathic medications, MAOIs, other antidepressants, antipsychotics, stimulants and mood stabilizers.
Statistical Methodology	 Statistical analysis plan for Primary objective and secondary objectives : Primary efficacy outcome, HAMD24, will be examined in a frequentist analysis (i.e., meta-analysis) combining the data obtained in this study with data borrowed from two prior randomized controlled trials conducted in adults tested using the same procedures outlines in this protocol (O'Reardon, et al., 2007; George, et al., 2010). The model for this analysis will include the following terms: treatment (active vs. sham), baseline score (continuous), medication resistance level as determined using the Antidepressant Treatment Record (ATR), (ATR=1 'Lo' vs. ATR=2-4 'Hi'), and Study (adolescent study, and adult studies O'Reardon, et al, 2007 and George, et al, 2010) as fixed effects, and, interaction terms for "study-by-treatment" and "ATHF medication resistance level-by-treatment". A random effect of "site nested within study" will also be included to assess any potential site effects. In the absence of a statistically significant interaction between Study and Treatment on the primary efficacy outcome variable at a pre-specified alpha level = 0.10, the continuity of efficacy across the age range 12 to 70 will be established, and the main effect for treatment is statistically significant at the alpha level = 0.05. A sample size of 50 patients per treatment condition in the adolescent study and an alpha level of 0.10 to test the Study by Treatment interaction, will detect a statistically significant Study by Treatment interaction if the mean treatment group difference, in favor of active, is greater than the upper bound of 5.5 points or less than the lower bound of -0.8 points. In the absence of a statistically significant interaction between Study and Treatment, the lower bound of the observed treatment group difference must be greater than 1.7 in favor of the active

treatment in order to borrow data from the adult studies in a meta-
analysis with the data from the adolescent study.

8 Introduction

This document is a protocol for a human research study. This study will be carried out in accordance with the procedures described in this protocol, applicable United States and Canadian government regulations and Good Clinical Practices, as documented in the study reference manual.

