The criteria above are clinically justified based on the results using the HAMD24 outcome measure in the prior adult studies which ranges from 1.7 to 2.5 (O'Reardon, et al, 2007; George, et al, 2010). The maximum Type I error rate of 15% for the adolescent data alone is justified given the large dataset available in adults (N=491) and that adult and adolescent populations should respond similarly to TMS Therapy. Simulations using data from the adult studies and N=100 adolescents, shows that with a type I error rate of 5%, the observed HAMD24 mean difference between active and sham treatment would need to be 2.67, which would require a result greater than what it would need to achieve had it been considered alone. For this reason, the 15% type I error rate for the adolescent data is justified.

If the criteria described above for pooling the adolescent study with the adult studies are not satisfied, the adolescent study must stand alone. If the results of the analysis of the adolescent study shows a statistically significant treatment group difference in favor of the active treatment at a pre-specified alpha level = 0.05, then this study alone will be sufficient to establish efficacy in the adolescent population.

A listing of the efficacy outcome measures and their intended sequence of testing in priority order are listed here. Note that the point of declaration of efficacy for the primary outcome measure is concealed from the Investigator and hence, is not specifically noted in this listing. All tests are to be performed on the intent to treat sample unless specifically noted. Please refer to the Schedule of Events for a listing of study timing for collection of primary and secondary outcome measures.

Primary Efficacy Outcome Measure	Definitions
HAMD24: total score, intent to treat	HAMD24 total score change from baseline value [Blinded
sample using last post-treatment score	point of declaration of efficacy for primary outcome
	measure included in statistical supplement]
Secondary Efficacy Outcome	
Measures	
Continuous outcomes	[Blinded point of declaration of efficacy for secondary
HAMD17, MADRS, CDRS-R, QIDS-	outcome measures included in statistical supplement]
A17-R, CGI-S: total score, intent to treat	
sample using last post-treatment score	
Responder categorical outcome	
HAMD (24 and 17 Item versions)	For HAMD, MADRS, CDRS-R, and QIDS-A17-SR:
MADRS	proportion of patient population achieving an end of acute

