#### **D.** Flow of Analysis:

First, the adolescent study data will be analyzed standing alone. If the results of the analysis of the adolescent study shows a statistically significant treatment group difference in favor of the active treatment at a pre-specified alpha level = 0.05, then this study alone will be sufficient to establish efficacy in the adolescent population. If the stand alone analysis does not have statistically significant results, the meta-analysis will be performed.

Based on this meta-analysis, there are 3 essential criteria to declare success and conclude that the evidence rejects the null hypothesis of no difference between active TMS and sham TMS in adolescent patients with treatment resistant major depressive disorder. These criteria are:

- 1) The main effect of treatment on the primary efficacy variable of mean change from baseline on the HAMD24 in the adolescent/adult studies meta-analysis will be statistically significant, and fall below the specified alpha level of 0.05,
- 2) There will be no statistically significant evidence of interaction between Study and Treatment on the primary efficacy outcome variable at the pre-specified alpha level  $\geq 0.10$ ,
- 3) The study-specific treatment effect observed for the primary efficacy outcome variable in the adolescent study as a stand-alone analysis will reside between the ranges of 1.7 points to 5.5 points on the HAMD24, and to meet the maximum Type I error rate of 15%.

The criteria above are clinically justified based on the results using the HAMD24 outcome measure in the prior adult studies which ranges from 1.7 to 2.5 (O'Reardon, et al, 2007; George, et al, 2010). The maximum Type I error rate of 15% for the adolescent data alone is justified given the large dataset available in adults (N=491) and that adult and adolescent populations should respond similarly to TMS Therapy. Simulations using data from the adult studies and N=100 adolescents, shows that with a type I error rate of 5%, the observed HAMD24 mean difference between active and sham treatment would need to be 2.67, which would require a result greater than what it would need to achieve had it been considered alone. For this reason, the 15% type I error rate for the adolescent data is justified.

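### A non-significant study-by-treatment test is read as establishing continuity of efficacy from age 12 to 70, although it would pass more often than not if TMS had no effect in adolescents

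*Protocol*

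**What the plan says.** The claim is in Protocol Section 7 (Study Summary, Statistical Methodology). If the Study-by-Treatment interaction is not significant at alpha 0.10, "the continuity of efficacy across the age range 12 to 70 will be established". The sentence goes on "and the main effect for treatment is statistically significant at the alpha level = 0.05", so a second condition, on the pooled data, is attached.

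The next item gives the operating range for 50 adolescents per arm and an interaction alpha of 0.10: the interaction comes out significant only when the adolescent result "is greater than the upper bound of 5.5 points or less than the lower bound of -0.8 points". The synopsis then adds that, even with no interaction, the adolescent difference must exceed 1.7 in favour of active before adult data are borrowed.

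Protocol Section 15.2 and SAP Section 2.D turn this into three joint criteria for success on the pooled route:

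1. A pooled main effect at 0.05.
2. "There will be no statistically significant evidence of interaction between Study and Treatment on the primary efficacy outcome variable", at 0.10.
3. An adolescent effect of 1.7 to 5.5 points, with a maximum type I error of 15%.

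The SAP runs the adolescent study alone first and goes to the pooled analysis only if that result is not significant. Neither document states the power of the interaction test, a HAMD24 SD, or an equivalence margin for the adolescent-adult difference.

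**The concern.** A test that does not reject shows similarity only if it had a good chance of rejecting when the groups truly differ. Here the difference that matters is TMS working in adults and not in adolescents. If the test usually misses that, its non-significance says little about ages 12 to 21. The attached main-effect condition is a weak guard because adults supply 491 of about 591 subjects.

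What is at stake is the wording of a paediatric efficacy claim. The synopsis presents continuity across the whole age range as a finding, on conditions that a device with no adolescent effect could often meet.

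**Working it through.** **Inputs**
- Adolescents: 50 per arm (Protocol Section 7). Adults: N=491, equal arms assumed (Protocol 15.2: "is justified given the large dataset available in adults (N=491").
- Adult HAMD24 effect: 1.7 to 2.5 points (Protocol 15.2: "prior adult studies which ranges from 1.7 to 2.5").
- Interaction alpha: 0.10, taken as two-sided, critical value 1.645.
- HAMD24 SD: not stated, so assumed. It is inferred in steps 1 and 2.

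**1. The plan's own bounds.** The interval -0.8 to 5.5 has centre 2.35, which lies inside the adult range, and half-width 3.15. So SE(interaction) = 3.15/1.645 = 1.915. With SE(interaction) = SD x sqrt(4/100 + 4/491) = 0.2194 x SD, the implied SD is 8.73.

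**2. A second SD from the documents.** Protocol 8.1 gives the NIMH-funded adult trial (N=197) a HAMD24 difference of -2.11, 95% CI -4.30 to 0.08. SE = (4.30 + 0.08)/(2 x 1.96) = 1.117, and SD = 1.117/sqrt(4/197) = 7.84. Put back into step 1 with centre 2.35, this gives bounds of -0.5 to 5.2, so the stated bounds are plausible. The 1.7 and 2.67 thresholds, read as one-sided 15% and 5% tests, imply SDs of 8.2 and 8.1, inside the range 7.84 to 8.73.

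**3. Chance of a non-significant interaction when the true adolescent effect is zero.** SE(adolescent) = 0.2 x SD. Holding the adult estimate fixed, the non-significance limits are adult effect ± 1.645 x 0.2194 x SD, that is ± 0.361 x SD. The probability is that of a normal variable with mean 0 and SE 0.2 x SD falling between them.

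| SD | Adult effect | Limits | P(non-significant), true effect 0 |
|---|---|---|---|
| 7.84 | 2.5 | -0.33 to 5.33 | 58.3% |
| 7.84 | 1.7 | -1.13 to 4.53 | 76.2% |
| 8.73 | 2.5 | -0.65 to 5.65 | 64.5% |
| 8.73 | 1.7 | -1.45 to 4.85 | 79.4% |

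Using the plan's bounds directly, P(-0.8 < observed < 5.5) is 68-69%. Letting the adult estimate vary as well gives 58-77%.

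**4. Adding the main-effect condition.** In a simulation with adolescent effect 0 and true adult effect 2.35, a non-significant interaction and a significant main effect occur together about 51-52% of the time if studies are weighted by information. The figure is about 22-25% if the two study groups are weighted equally.

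**5. Adolescent sample for 80% power to separate 0 from 2.35.** Solve SD² x (2/n + 4/491) = (2.35/(1.645 + 0.842))². This gives n of about 313 per arm (SD 7.84) to 559 (SD 8.73), against 50 planned.

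**6. What the 1.7 to 5.5 criterion does.** With true effect 0, P(1.7 < observed < 5.5) is 13.9% (SE 1.57) to 16.4% (SE 1.75). Simulating all three criteria together gives about 13-16%.

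**7. What criterion 2 adds to criterion 3.** On the low side it adds nothing: every lower limit in step 3 is below zero, and the floor is 1.7. On the high side, the SAP's order sends to the pooled step only effects that are non-significant alone, so at most 1.96 x 0.2 x SD = 0.392 x SD, or 3.1 to 3.4 points. The upper limits in step 3 are 4.5 to 5.7.

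**The case against.** The strongest reply is that the plan never decides on the interaction test by itself. A reader might infer that the licence to borrow adult data rests on this weak test, or that zero and slightly harmful observed effects qualify for success. The documents do not support that. The synopsis requires more than 1.7 points before borrowing, and Protocol 15.2 and SAP 2.D require 1.7 to 5.5 as a joint criterion. The plan also openly accepts a 15% error rate on the adolescent data, and step 6 lands close to it. Whether 15% is acceptable is a separate question. This part of the reply stands, and it limits the consequence of the point.

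A reader might also infer that criterion 2 can never fail once criterion 3 is met, because 1.7 to 5.5 lies inside -0.8 to 5.5. That goes too far. Those bounds are planning values. The actual test will use the observed variance and adult estimate, in a model with site, baseline and resistance-by-treatment terms. Three of the four upper limits in step 3 are below 5.5, so an observed 5.4 could meet criterion 3 and fail criterion 2. The synopsis can also be read as giving Study three levels, in which case a difference between the adult trials could trigger the test.

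Finally, the continuity sentence is in the synopsis only. SAP 2.D lists non-significance as a condition and does not say that it establishes continuity. That is correct, but the sentence remains in the Protocol, it does not contain the 1.7 floor, and the main-effect condition it does contain comes mostly from adult data.

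**Conclusion.** The synopsis inference is wrong as written. Under no adolescent effect the interaction test would be non-significant about 58-79% of the time, so it cannot establish continuity of efficacy down to age 12. This rests on a normal approximation, equal adult arms, an adult effect of 1.7 to 2.5 and an SD of 7.84 to 8.73 inferred from the documents' own figures. The conclusion is not sensitive to the SD: at SD 10, letting the adult estimate vary, non-significance is 69-80%.

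The effect on the decision rule is limited. The 1.7-point floor, not the interaction test, holds the chance of passing with no true adolescent effect to roughly 14-16%. Criterion 2 adds no protection on the low side and, under the SAP's stand-alone-first order, is unlikely to fail on the high side. It is not strictly implied by criterion 3.

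**What to change.** - In the Protocol synopsis, replace the conclusion that continuity is established with a statement that no difference between adolescents and adults was detected.
- In the Protocol and SAP, add the adolescent-minus-adult treatment difference with its 90% CI to the reported results.
- Beside any claim for ages 12 to 70, report the adolescent-specific estimate with its 95% CI, for information and not as a new decision rule.
- State that the 1.7-point floor, not the non-significant interaction, is the safeguard against an absent adolescent effect. Do not state that criterion 2 follows from criterion 3.

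The cost is a wording change in both documents and two reported intervals. No patients, data collection or success criteria change. The age-range claim becomes more modest.
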